## **9. STATISTICAL CONSIDERATIONS**

This is an open-label Phase 1/2 multi-arm study. The primary objective in Phase 1 is to determine the Maximum Tolerable Dose (MTD) and identify the Recommended Phase 2 Dose (RP2D) of DS-1594b.

Phase 2 will evaluate the safety and response rate within 3 months of therapy initiation with single agent or combinations of DS-1594b at the RP2D in the following 4 cohorts:

- Cohort A: R/R AML with MLL-rearrangement,
- Cohort B: R/R AML with NPM1 mutation,
- Cohort C: R/R AML treated with the combination of azacitidine and venetoclax with DS-1594b

- Cohort D: R/R ALL treated with the combination of miniHCVD with DS-1594b.

Up to 182 subjects will be enrolled in the study (approximately 66 subjects in Phase 1 (i.e. up to 42 for dose titration-BOIN design, 6 for food effect sub-studies, and up to 18 for refining RP2D at safe doses below or at the MTD and DDI sub-studies) and up to 26 subjects per cohort in Cohorts A-and B and up to 32 subjects per cohort in Cohorts C and D in Phase 2).

### **9.1. Phase 1**

The primary objective of Phase 1 is to determine the MTD and RP2D of DS-1594b when administered as a single agent in subjects with R/R AML or R/R ALL, including subjects with or without MLLr or NPM1m using a Bayesian optimal interval (BOIN) design (Liu and Yuan, 2015; Yuan et al., 2016) to find the MTD. The details of the BOIN design to be used in the Phase 1 are outlined in Section 3.2.

According to the BOIN design, cohorts of 3 subjects will be treated at each dose level. If a dose level is found to be safe by the BOIN design we will escalate to the next higher dose level. Evaluation for above mentioned BOIN rule will be done for each dose level and dosing regimen (i.e., QD vs BID) separately based on the cumulative number of DLT evaluable subjects treated in that dose level. In case the multiple dosing regimens are initiated simultaneously and parallel enrollment is allowed in the multiple dosing regimens, the evaluation for BOIN rule for each dose level and dosing regimen would be made separately. Up to 9 additional subjects may be enrolled at each dose level that has already been deemed to be safe with the intent to gain additional information on safety and efficacy at different dose levels, to guide selection of optimal biologically effective RP2D. Although all R/R ALL and R/R AML subjects, irrespective of mutations, will be allowed during the Phase 1 dose-escalation it is suggested that at least 3 subjects with MLLr or NPM1m are included at each dose level that is anticipated to be clinically active, to allow for optimal evaluation of safety and efficacy in the presumed target population to guide selection of the optimal RP2D. As described in Section 3.2, we will use the same the elimination boundaries in Table 4 for the toxicity monitoring in the expansion cohort(s).

### **9.2. Phase 2**

The primary endpoint of cohorts A-C is the achievement of CR + CRh within 3 months of therapy initiation in subjects with R/R AML with MLLr or NPM1m. The primary endpoint of cohort D is the achievement of CR + CRI within 3 months of therapy initiation in subjects with R/R ALL with MLLr. Up to 26 subjects will be enrolled per cohort in Cohorts A and B and up to 32 subjects will be enrolled per cohort in Cohorts C and D. Each cohort will be analyzed separately. Treatment will be considered encouraging if the CR/CRh rate (Cohorts A, B, and C) or CR/CRI rate (Cohort D) rate would reach at least 40%, an improvement over the historical rate by more than 15%. The study will monitor futility and toxicity using the Bayesian method of Thall, Simon and Estey.

### **9.3. Futility and Toxicity Monitoring**

The historical data suggest a response rate of 25% in subjects with R/R AML or R/R ALL with NPM1m or MLLr using a variety of different therapies, and the target response rate is

40% with acceptable safety. The response rate is defined as CR + CRh rate within 3 months of therapy initiation in cohorts A, B and C and CR/CRi rate within 3 months of therapy initiation in Cohort D. The cohort will be stopped early if the data suggest that:

$$\Pr(P_E \leq 0.40 | \text{data}) > 0.95, \text{ or}$$

$$\Pr(P_T > 0.2 | \text{data}) > 0.85.$$

where  $P_E$  is the response rate and  $P_T$  is the probability of DLT for experimental treatments, respectively. We assume  $P_E$  and  $P_T$  follow a priori  $\sim \text{beta}(0.5, 0.5)$ . That is, if at any time during the study we determine that there is more than 95% chance that the response rate would be at less than 40%, the cohort will be stopped due to futility. Or if at any time during the study, we determine that there is more than 85% chance that the toxicity rate is more than 20%, the cohort will be stopped due to toxicity. DLT observations from IPDE will not be used in toxicity monitoring.

The futility and toxicity monitoring will be conducted separately for each of four cohorts, starting once the 10th subject in a cohort has been evaluated, and thereafter in groups of 5 subjects, except the last group. The design parameters are set the same for cohorts A-D, each with a maximum of 26 subjects per cohort, excluding the safety run-in period for the first 6 subjects in each of Cohorts C and D (Section 3.3).

The stopping boundaries for futility and toxicity based on these assumptions and monitoring conditions are provided in [Table 22](#)[Table 22](#). The operating characteristics are summarized in [Table 23](#)[Table 23](#) and in [Table 24](#)[Table 24](#) for futility and toxicity monitoring, respectively. [Table 25](#)[Table 25](#) presents the overall early stopping probabilities for futility and toxicity monitoring. Bayesian Toxicity Monitoring software and Bayesian Efficacy monitoring with Posterior Probability software on <https://trialdesign.org> were used for the design of toxicity and futility monitoring.

If the study arm is not stopped early and 26 subjects have been treated and evaluated in each cohort, assuming 11 of the 26 subjects achieve CR+CRh (Cohorts A, B, C) or CR+CRi (Cohort D), then the 95% credible interval for CR+CRh (Cohorts A-C) or CR+CRi (Cohort D) rate will be (25%, 61.3%).

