## 3.3. Phase 2 Design

Enrollment in Phase 2 will start once the RP2D has been determined in Phase 1. This Phase 2 study will have four cohorts:

- Cohort A: DS-1594b monotherapy for R/R AML with MLL-r,
- Cohort B: DS-1594b monotherapy for R/R AML with NPM1m,
- Cohort C: DS-1594b in combination with azacitidine and venetoclax for R/R AML with NPM1m or MLLr
- Cohort D: DS-1594b in combination of mini-HCVD for R/R ALL with MLLr

Subjects enrolled in Cohorts A and B will receive the RP2D dose of DS-1594b determined in Phase 1. Cohorts C and D will enroll an initial 6 subjects in a safety run-in at one dose level below the RP2D (Dose level 0) with DS-1594b dose titration as specified below.

Cohorts A and B (single agent cohorts) will enroll a maximum of 26 subjects, and Cohorts C and D (combination cohorts) will enroll a maximum of 32 subjects, to allow reasonable determination of CRc within 3 months of therapy initiation.

For the combination cohorts (C & D) there will be a safety-run in evaluation with pre-defined toxicity stopping rules to be implemented for early DLT evaluation as per following plan:

- Safety run-in evaluation by the Safety Review Committee of the first 6 subjects in cohorts C and D will occur after 6 subjects have completed at least one cycle of treatment (or at least 28 days from the first day of treatment).
- Enrollment will be paused while the first 6 subjects are evaluated for safety. Each combination cohort will be evaluated independently.
  - If  $\leq 1$  of the 6 subjects experiences DLT in the first cycle of treatment, the treatment combination will be considered as safe and the DS-1594b dose can be escalated to the RP2D (Dose level 1) for the treatment of the next 6 patients (repeat the safety run-in evaluation). If the RP2D (Dose level 1) is considered safe, continue enrollment of an additional 20 subjects at the RP2D (i.e. total subjects treated at the RP2D will be 26 subjects; total cohort size will be 32 subjects). If  $\geq 2$  of 6 subjects at the RP2D experiences DLT in the first cycle of treatment, de-escalate and continue enrollment of an additional 20 subjects at Dose Level 0.

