**Table 22: Stopping Boundaries for Toxicity and Futility Monitoring in Each of Cohorts A-D**

	Toxicity Stopping Boundaries		Futility Early Stopping Boundaries	
Number of Subjects (inclusive)	Num DLTs (inclusive) are considered too toxic	Actions for toxicity monitoring	Num. Responses (inclusive) are considered futile	Actions for futility monitoring
10	4 - 10	Early stopping	0 - 1	Early stopping
15	5 - 15	Early stopping	0 - 2	Early stopping
20	6 - 20	Early stopping	0 - 4	Early stopping
26	8 - 26	Reach to Nmax	0 - 6	Reach to Nmax

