**Table 23: Operating Characteristics for Futility Monitoring in each of Cohorts A-D**

True Response Rate	Early stop probability for futility	Average sample size
0.1	0.9633	12.29
0.2	0.6713	17.72
0.3	0.2906	22.57
0.4	0.0811	25.00
0.5	0.0153	25.79
0.6	0.002	25.97

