**Table 24: Operating Characteristics for Toxicity Monitoring in each of Cohorts A-D**

True DLT rate	Probability of Early Stop for toxicity	Average Sample size
0.1	0.0235	25.70
0.2	0.2509	22.92
0.3	0.636	17.84
0.4	0.8954	13.53
0.5	0.9834	11.22

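### Section 9.3 words both stops as 'at any time' although only the looks at 10, 15 and 20 operate, and under those looks Cohorts A and B can enrol after a toxicity stop is certain

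*Combined protocol and SAP*

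**What the plan says.** Section 9.3 gives the toxicity stop in these terms: "if at any time during the study, we determine that there is more than 85% chance that the toxicity rate is more than 20" per cent, the cohort stops. The futility stop is worded in the same way, "if at any time during the study we determine that there is more than 95% chance that the response rate" is below 40%.

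The following paragraph sets a schedule for both outcomes, "starting once the 10th subject in a cohort has been evaluated, and thereafter in groups of 5 subjects", with a different size for the last group and a maximum of 26. It then says: "The stopping boundaries for futility and toxicity based on these assumptions and monitoring conditions are provided in" Table 22. That table has rows only at 10, 15, 20 and 26 subjects, and the row at 26 is the end of enrolment, not an early stop. Its toxicity column, "Num DLTs (inclusive) are considered too toxic", starts at 4, 5 and 6 DLTs for the three early looks. The futility column ends at 1, 2 and 4 responses.

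On starting dose, Section 3.3 says: "Subjects enrolled in Cohorts A and B will receive the RP2D dose of DS-1594b determined in Phase 1". The six-subject run-in and its enrolment pause are written for Cohorts C and D only. Section 3.3.1 points to Section 9.3 as the pre-specified toxicity criteria for all cohorts. Beyond that, Section 9.3.1 gives the Safety Review Committee (SRC) safety oversight, and Section 8.9.2 lets the investigator and sponsor terminate the study. Neither carries a numeric threshold.

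**The concern.** Two things follow, one from each reading of the rule.

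First, the sentences that turn the posterior criteria into action describe continuous checking, while the tables describe three looks. A committee that applied the sentences as written would stop more cohorts than the protocol says it will, for both outcomes.

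Second, if the looks govern, a cumulative DLT count cannot fall. Once there are 4 DLTs among the first 10 subjects, 5 among the first 15 or 6 among the first 20, the stop at the next look is settled. No stated numeric rule halts enrolment between that moment and the look. In Cohorts A and B, which go straight to the RP2D, subjects could start a treatment that the plan's own rule is already bound to stop.

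**Working it through.** **Inputs (Section 9.3, Table 22).** Prior beta(0.5, 0.5) for both rates. Toxicity: stop if Pr(P_T > 0.20 | data) > 0.85. Futility: stop if Pr(P_E ≤ 0.40 | data) > 0.95. Early looks at n = 10, 15 and 20; maximum 26.

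**Step 1: boundaries.** With x events in n subjects the posterior is beta(0.5 + x, 0.5 + n − x).

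- Toxicity, Pr(P_T > 0.20): 3/10 gives 0.795 and 4/10 gives 0.934; 4/15 gives 0.753 and 5/15 gives 0.897; 5/20 gives 0.725 and 6/20 gives 0.867. The boundaries are 4, 5 and 6, as in Table 22.
- Futility, Pr(P_E ≤ 0.40): 1/10 gives 0.981 and 2/10 gives 0.906; 2/15 gives 0.987 and 3/15 gives 0.948; 4/20 gives 0.970 and 5/20 gives 0.918. The boundaries are 1, 2 and 4, as in Table 22.

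**Step 2: the plan's own operating characteristics.** Exact binomial recursion: carry the distribution of the event count forward one subject at a time, remove the probability at or beyond a boundary at n = 10, 15 and 20, and sum what was removed. Average N is the sum of n × P(stop at n), plus 26 × P(no early stop). At a 20% DLT rate the stops are 0.1209 at 10, 0.0722 at 15 and 0.0578 at 20, which sum to 0.2509. Average N = 10(0.1209) + 15(0.0722) + 20(0.0578) + 26(0.7491) = 22.92. All five rows of Table 24 reproduce this way. Table 23 also reproduces, for example 0.0811 and N 25.00 at a 40% response rate. Table 25 is 1 − (1 − futility stop)(1 − toxicity stop), to within 0.0001. The three looks are therefore the operative design.

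**Step 3: the 'at any time' wording.** The same recursion, applying the posterior criterion after every subject from the 10th:

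| | Looks at 10, 15, 20 (stated) | Every subject from the 10th |
|---|---|---|
| Toxicity stop, true DLT rate 20% | 25.1% | 31.4% |
| Toxicity stop, true DLT rate 30% | 63.6% | 71.7% |
| Futility stop, true response rate 40% | 8.1% | 15.0% |

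**Step 4: enrolment after certainty.** Between looks, 3 DLTs in 10 subjects followed by DLTs in subjects 11 and 12 make the stop at 15 certain, with three subjects still to enrol. Before the first look, the chance that 4 or more DLTs have occurred in 9 subjects, P(X ≥ 4) with X ~ Bin(9, p), is 8.6%, 27.0%, 51.7% and 74.6% at p = 20%, 30%, 40% and 50%.

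Now stop as soon as the count reaches the next look's boundary (4 up to subject 10, 5 up to 15, 6 up to 20), taking each DLT as known before the next subject starts:

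| True DLT rate | Stop probability, both rules | Average N, looks | Average N, stop when certain | Difference |
|---|---|---|---|---|
| 10% | 0.0235 | 25.70 | 25.67 | 0.03 |
| 20% | 0.2509 | 22.92 | 22.59 | 0.34 |
| 30% | 0.636 | 17.84 | 16.80 | 1.04 |
| 40% | 0.8954 | 13.53 | 11.64 | 1.89 |
| 50% | 0.9834 | 11.22 | 8.50 | 2.72 |

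Differences come from unrounded values (at 20%, 22.925 − 22.587 = 0.338). The stop probabilities are identical because the rule only brings forward a stop that would occur anyway.

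**The case against.** The strongest reply is that the two halves cannot both bite in one trial. If the 'at any time' sentence is followed, there is no late stop: 4/9 has posterior 0.957, 5/14 has 0.922 and 6/19 has 0.893, all above 0.85. That is right. The late stop exists only under the look-based reading. But the look-based reading is the one the schedule and every table support, so the sentence cannot be counted on as the safeguard.

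A second reply is that the wording conflict resolves itself, since 'at any time' may be shorthand for any scheduled look. That also has force: Tables 22 to 25 are correct, and this is a wording conflict, not a calculation error. A reader might go further and take the sentence to mean checking from the first subject, which would give a 53.7% toxicity stop at a true 20% DLT rate and a 23.9% futility stop at a true 40% response rate. The documents do not support that, because monitoring is said to begin with the 10th evaluated subject.

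Third, the RP2D comes from a Phase 1 that targets a 20% DLT rate, where the gain is 0.34 of a subject. An SRC that saw 4 DLTs in 8 subjects would have clear grounds to act. This stands as to size. It does not replace a threshold: SRC, investigator and sponsor action is discretionary, whereas Section 3.3.1 relies on pre-specified criteria.

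Fourth, limiting the sentence to the Table 22 counts gives up text that, taken literally, would act on 2 DLTs in 3 (posterior 0.966) or 3 in 6 (0.956). True of the literal text, but the operative looks do not act there either.

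**Conclusion.** The point holds, at modest size. The 'at any time' sentences do not match the schedule or the stated operating characteristics. The fair measure of the mismatch is 31.4% against 25.1% for toxicity and 15.0% against 8.1% for futility, at the rates given above. Under the operative looks, Cohorts A and B have no numeric trigger between the moment a toxicity stop becomes certain and the look that declares it. The average cost is 0.34 subjects per cohort at the 20% target rate and 2.72 at 50%.

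Those averages assume that each DLT is known before the next subject starts. It would be easy to call them upper limits, but the documents do not allow that. A lag in learning of DLTs would reduce what an immediate stop saves, while continued enrolment during evaluation could carry a cohort past the look and make the over-run larger. Accrual, pausing and reporting lag are not stated. A reader might also infer that the toxicity look must wait for the 3-month response endpoint because the schedule is shared. The plan does not say so, and it does not say otherwise. Nor are Cohorts A and B without any safety oversight; what they lack is a pre-specified count that acts between looks.

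**What to change.** Change two sentences in Section 9.3.

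- Futility: replace 'at any time during the study' with *at each scheduled look (10, 15 and 20 subjects)*.
- Toxicity: *The 0.85 criterion is applied through the Table 22 counts. Enrolment in a cohort stops as soon as the cumulative DLT count reaches the boundary of the next scheduled look (4 within the first 10 subjects, 5 within the first 15, 6 within the first 20), without waiting for that look or for response evaluation.*

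In Table 24, replace the average sample sizes with 25.67, 22.59, 16.80, 11.64 and 8.50. The column "Probability of Early Stop for toxicity" does not change, nor do Tables 22, 23 and 25. No subjects or data items are added.

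The limit of this change should be stated with it: it does not act on fewer than 4 DLTs. A check before that point would be a separate design choice and would require Tables 24 and 25 to be recomputed.

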  - If  $\geq 2$  of 6 subjects have DLTs in the first cycle of treatment at Dose Level 0, then an additional 6 subjects will enroll at a next lower dose level to be determined by the Principal Investigator and Safety Review Committee after reviewing the safety, efficacy, and PD data from the first 6 subjects enrolled ([Table 6](#)[Table 6](#), [Table 7](#)[Table 7](#)). If  $\leq 1$  of the additional 6 subjects treated at the lower dose level experience DLTs, this treatment combination will be considered as safe and continue to enroll to a total of 26 subjects (i.e. an additional 20 subjects at the lower dose level; total cohort enrollment of 32 subjects). If  $\geq 2$  of these 6 additional subjects experienced DLTs, then enrollment at the current dose level will be closed.
- Subjects must receive at least 75% of the doses of DS-1594b, azacitidine (Phase 2 only), venetoclax (Phase 2 only), or miniHCVD (Phase 2) during the first 28 days on trial (i.e. during Cycle 1) to be considered evaluable during the DLT evaluation period. Any subjects who are not evaluable for DLT in either cohort during the safety-run in period will be replaced for the assessment of DLT rate. This will allow for early identification of significant toxicities and early stoppage in the combination cohorts.
- The Safety Review Committee (SRC) will meet when there are enough DLT-evaluable subjects to review in each cohort who have completed the DLT evaluation period. The SRC will review the DLT data, other AE data, and available PK/PD, ECG, and laboratory data before proceeding to expansion of each of the cohorts to enroll the additional 20 subjects.

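### In Cohorts C and D, if Dose Level 0 passes its run-in and the RP2D fails, Section 9.3 monitors Dose Level 0 using 6 subjects from the abandoned dose and drops 6 from the kept one

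*Combined protocol and SAP*

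**What the plan says.** Section 9.3 gives all four cohorts the same monitoring design: at most 26 subjects, with looks at 10, 15 and 20 and completion at 26. For the combination cohorts it adds "excluding the safety run-in period for the first 6 subjects in each of Cohorts C and D". The exclusion does not depend on how the run-in turns out.

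Section 3.3 starts Cohorts C and D with 6 subjects at Dose Level 0, one level below the RP2D. Three paths then lead to a full cohort of 32:

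- Dose Level 0 has at most 1 DLT in 6, and so does the RP2D. Enrolment continues at the RP2D: "total subjects treated at the RP2D will be 26 subjects; total cohort size will be 32 subjects".
- Dose Level 0 passes but the RP2D has 2 or more DLTs in 6. The instruction is to "de-escalate and continue enrollment of an additional 20 subjects at Dose Level 0".
- Dose Level 0 fails and the next lower level passes. Then "this treatment combination will be considered as safe and continue to enroll to a total of 26 subjects", made up with "an additional 20 subjects at the lower dose level; total cohort enrollment of 32 subjects".

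Section 9 describes Phase 2 as evaluating "single agent or combinations of DS-1594b at the RP2D in the following 4 cohorts", which leaves no room for a combination cohort that finishes below the RP2D.

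**The concern.** Dropping the first 6 gives the right set on the first and third paths: the remaining 26 are all at the dose carried forward. On the second path it does not. The kept dose is Dose Level 0, its 26 subjects are numbers 1–6 and 13–32, and the rule selects numbers 7–32.

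**Toxicity.** The 6 RP2D subjects bring at least 2 DLTs by definition, because that is why the RP2D was given up. Those DLTs count against the dose that was kept. With 4 or more, the boundary at the first look is met regardless of Dose Level 0, so Section 9.3 stops a cohort that Section 3.3 says to continue.

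**Futility.** The direction depends on response by dose. If response is higher at the RP2D, its 6 subjects can hide futility at Dose Level 0. If it is lower, they can stop Dose Level 0 wrongly.

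**Working it through.** **Inputs from the plan (Section 9.3, Table 22).** Beta(0.5, 0.5) priors. Stop for toxicity if Pr(P_T > 0.2 | data) > 0.85, and for futility if Pr(P_E ≤ 0.40 | data) > 0.95. Early-stop boundaries at n = 10, 15, 20 are 4, 5, 6 or more DLTs, and 1, 2, 4 or fewer responses.

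**Reproducing the plan.** An exact binomial recursion over the three looks, starting from 0 subjects, gives toxicity stops of 0.0235, 0.2509, 0.636, 0.8954 and 0.9834 at DLT rates of 0.1 to 0.5 (Table 24). It gives futility stops of 0.9633, 0.6713, 0.2906, 0.0811, 0.0153 and 0.002 at response rates of 0.1 to 0.6 (Table 23). All agree with the plan. The tables are correct for 26 subjects at one dose.

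**Counting subjects.** In each path 32 − 6 = 26 are monitored: 26 at the RP2D; or 6 at the RP2D plus 20 at Dose Level 0; or 26 at the lower level. Excluding both run-in groups on the second path would leave 32 − 12 = 20, not the stated 26.

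**First look, no rates assumed.** The tenth monitored subject is taken as the end of the first look, so the look holds 6 carried-in subjects and 4 later Dose Level 0 subjects.

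- As written, 2, 3 or ≥4 RP2D DLTs lead to a stop after 2, 1 or 0 DLTs in those 4. For example, 2 + 2 = 4/10, with posterior probability 0.934 > 0.85.
- Dose-matched, at most 1 DLT is carried in. With 2 in the next 4 that is at most 3/10, with posterior probability 0.795, so the cohort continues.

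**Toxicity stop within the branch.** The documents give no DLT rates for the combinations, so p0 (Dose Level 0) and p1 (RP2D) are assumptions.

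- As written: start from Binomial(6, p1) given ≥2, then add subjects at p0.
- Dose-matched: start from Binomial(6, p0) given ≤1, then add subjects at p0.
- Branch probability = P(≤1/6 at p0) × P(≥2/6 at p1).
- Conflict probability = P(≤1/6 at p0) × P(≥4/6 at p1).
- Excess per cohort = branch probability × difference in stop probability.

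Worked case, p0 = 10%, p1 = 30%:

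- Branch: 0.8857 × 0.5798 = 0.514.
- Given ≥2, the RP2D group has 2, 3 or ≥4 DLTs with probability 0.559, 0.319 and 0.122. The later stop probabilities are 0.0969, 0.4182 and 1. Total: 0.0542 + 0.1336 + 0.1215 = 0.309.
- Given ≤1, the Dose Level 0 group has 0 or 1 DLT with probability 0.6 and 0.4. The later stop probabilities are 0.0020 and 0.0156. Total: 0.0012 + 0.0062 = 0.0074.
- Excess: 0.514 × (0.309 − 0.007) = 15.5 points.

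| p0 / p1 | Branch prob. | Stop as written | Stop dose-matched | Excess, points (vs Table 24 design) | ≥4/6 conflict |
|---|---|---|---|---|---|
| 5% / 15% | 0.22 | 8.1% | 0.03% | 1.7 (1.7) | 0.6% |
| 10% / 20% | 0.31 | 21.8% | 0.7% | 6.4 (5.9) | 1.5% |
| 10% / 30% | 0.51 | 30.9% | 0.7% | 15.5 (14.7) | 6.2% |
| 20% / 30% | 0.38 | 58.3% | 11.4% | 17.8 (12.6) | 4.6% |

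The figure in brackets replaces the dose-matched stop with the unconditional one at p0. With equal rates the excess is 1.4 (1.3) points at 10%/10% and 8.9 (5.9) at 20%/20%. That part comes from conditioning on opposite run-in results and not from a real difference between doses.

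**Futility.** Response rates are assumed, and response is taken as independent of DLT. Start from Binomial(6, r1), then add subjects at r0.

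| r0 / r1 | Stop as written | Stop with 26 at Dose Level 0 |
|---|---|---|
| 20% / 40% | 38.7% | 67.1% |
| 30% / 40% | 18.6% | 29.1% |
| 40% / 20% | 23.9% | 8.1% |
| 40% / 40% | 8.1% | 8.1% |

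**The case against.** The clause can be read as sample-size bookkeeping, 32 minus 6, explaining why one Table 22 serves all cohorts. Section 3.3 builds each continuing path to 26 at the kept dose, so the intent is probably dose-matched. That reading of intent is fair, but no passage defines a set for this path. The words as they stand give either the mixture or, if both run-in groups are excluded, 20 subjects instead of 26.

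The within-branch contrasts are enlarged because one set is conditioned on at least 2 DLTs and the other on at most 1. This stands, and it is why the equal-rate results are shown. All rates are assumed, the largest effects need a 30% rate at the RP2D, and the certain-stop conflict has probability 0.6% to 6.2% in the four unequal-rate scenarios.

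The first-look figures also depend on counting the tenth monitored subject, not the tenth enrolled. Counting by enrolment would put the first look inside the RP2D run-in.

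The dose-matched set has a cost. Given a passed run-in it stops less often than Table 24 shows, and at a true 30% DLT rate less often than monitoring only the later 20 (39.0% against 51.8%). Figures that include the run-in gate do not describe protection once the gate has been passed. This stands and should be disclosed.

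Safety Review Committee review before the last 20 are enrolled helps, but does not say which subjects enter the stopping rule.

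**Conclusion.** The point holds. It is confined to one of the three continuing paths, where the literal rule applies the stopping boundaries to a mixture of two doses and omits 6 subjects at the dose being continued. The first-look consequence needs no assumed rates, only that the look falls at the tenth monitored subject. With 4 or more RP2D DLTs, Sections 3.3 and 9.3 contradict each other outright.

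Over the four unequal-rate scenarios the path has probability 0.22 to 0.51, and the excess early toxicity stopping per cohort is 1.7 to 17.8 points (1.7 to 14.7 against the unconditional design). Futility stopping may move either way and does not change when response is equal at the two doses. Tables 22 to 25 are not wrong; they do not describe this path. It should be corrected before the run-in data are seen, because choosing the set afterwards would make the stopping decision data-driven.

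**What to change.** Reconcile Sections 3.3 and 9.3 by replacing the exclusion clause with:

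*In Cohorts C and D the monitored set is the up to 26 subjects treated at the dose level carried forward under Section 3.3, including the 6 run-in subjects at that level; the 6 subjects at the other level are summarised separately.*

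Table 22 stays as it is, since its boundaries depend only on the number evaluated and the count, and the maximum remains 26. No dose or clinical rule changes.

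Label Tables 24 and 25 as not conditional on a passed run-in, or add a conditional toxicity column for Cohorts C and D:

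| True DLT rate | Table 24 | Dose-matched, given ≤1/6 | Fails run-in or stops early | Later 20 only (looks at 10, 15) |
|---|---|---|---|---|
| 10% | 2.35% | 0.7% | 12.1% | 1.9% |
| 20% | 25.09% | 11.4% | 42.0% | 19.3% |
| 30% | 63.6% | 39.0% | 74.4% | 51.8% |
| 40% | 89.54% | 70.1% | 93.0% | 80.2% |
| 50% | 98.34% | 90.2% | 98.9% | 94.7% |

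The fourth column is P(≥2/6) + P(≤1/6) × conditional stop; at 20%, 0.3446 + 0.6554 × 0.1145 = 0.420. Counting the run-in, overall protection at a level is not below Table 24. Monitoring only the later 20 is possible, but it discards 6 subjects at the kept dose and does not match the stated 26.

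The cost is one sentence and a label or extra column, with no added subjects or data. The plan should say openly that stopping after a passed run-in is less frequent than Table 24.
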